12.1.6 Analysis Approach

Demographics and Baseline Characteristics

Differences between the four study treatment groups in continuous baseline characteristics (i.e. age, percent bone required to be regenerated) will be analyzed using ANOVA. Differences between treatment groups in categorical baseline characteristics (i.e. gender, race, smoking history) will be analyzed using a two-sided, generalized, Fisher Exact test. Differences between ordinal outcomes (i.e. number of teeth to be implanted) will be analyzed using a singly ordered exact Kruskal-Wallis test as a global test of equality. Analyses will account for baseline smoking habit.

If any treatment groups are found to be imbalanced with respect to any baseline covariates based on test at a 0.05 alpha level, impact to the comparisons between the study treatment groups will be investigated by including those covariates in sensitivity analyses for the binary effectiveness analyses using a logistic regression model and for continuous effectiveness endpoints using an ANCOVA model.

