5.2 Justification for Study Design and Endpoints

5.2.1 Study Design

The randomization of the investigational device kits will be performed by [REDACTED] for the allocation of subjects at each investigational site. Subjects will be randomized to one of four groups so that treatment is balanced within each center by block randomization method stratified by smoking status. Enrollment will be defined as randomization to one of the above-mentioned study arms (Treatment I ~ IV). The randomization will be performed intraoperatively after surgeons confirm if the probing bone depth and the number of bony wall of defect of the target site meets the inclusion criteria (greater than 4 mm and at least one bony wall).

The active control arm (β -TCP alone) will be used for comparisons to three test groups with different rh-bFGF concentrations (0.1%, 0.3% and 0.4%) in order to determine the optimal concentration of rh-bFGF in combination with β -TCP to treat a qualifying periodontal defect.

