6.0 SELECTION AND DISCONTINUATION/WITHDRAWAL OF SUBJECTS

6.1 Inclusion Criteria

Subjects must meet all of the following criteria to be entered into the study:

1. Male or female, age of 25 and older
2. Must have read, understood, and signed a consent form
3. Must be able and willing to follow study procedures and instructions
4. Must have undergone thorough scaling and root planing of the target tooth and be expected to demonstrate good plaque control after instruction in oral hygiene
5. The target tooth must exhibit the following:
 - A pocket depth of 7 mm or greater
 - After surgical debridement, 4 mm or greater intrabony defect with at least 1 bony wall
 - Sufficient keratinized tissue to allow complete tissue coverage of the defect
 - Radiographic base of defect at least 3 mm coronal to the apex of the tooth

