8.0 STUDY PLAN

8.1 Study Procedures

The following sections describe the study procedures and data to be collected. Subjects will be assessed at the screening (Visit 1) and baseline (Visit 4) visits to determine and confirm eligibility. The identified target teeth at the screening visit (Visit 1) will be reconfirmed intra-operatively at the surgery visit (Visit 5), and one eligible tooth will be selected to receive the study treatment. Within 2 months prior to the study treatment, each subject will undergo thorough scaling and planing of all teeth in the target tooth's quadrant to control the disease process and minimize lesion variability (Visit 2 and if necessary, Visit 3). Note that a patient may have already undergone scaling and planing prior to screening. After study treatment, each subject will be monitored at periodic intervals to assess safety and effectiveness for at least six months. The Schedule of Study Procedures is located in Appendix A.

The Investigator and all study personnel will be blinded to the treatment. Only calibrated Examiners who are different from the surgeon performing the implantation should carry out the clinical evaluations to assess the study safety and effectiveness parameters. See Section 8.2 for calibration details.

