8.3.4 Visit 5: Periodontal Surgery and Implantation of Investigational Device

Pre-surgical procedure:

- Collect blood serum sample for rh-bFGF antibody; and,

Periodontal surgery:

Beginning with the target tooth ranked as the most severe disease, the area selected for surgery is anesthetized. Following intracrevicular incisions, buccal and lingual full-thickness horizontal (mucoperiosteal) flaps are raised extending at least one tooth mesial and distal to the treated tooth. In case of a missing proximal tooth, the flap is extended at least 6 mm proximal to allow easier management and placement of the test material. Care is taken to preserve as much as possible of the keratinized gingival connective tissue in the flap. A horizontal releasing incision will be performed in order to facilitate coronal displacement of the flap, if it is applicable. The inner

surface of the flap may be carefully instrumented to remove dento-gingival epithelium and granulation tissue.

Following the reflection of the mucoperiosteal flap, all granulation tissue associated with the osseous defect is removed. Meticulous root planing should be performed to remove subgingival soft and hard deposits on the root surfaces. Magnification aids and fiber optic lights for additional illumination should be utilized. Additionally, both hand and ultrasonic instruments are to be used to assure thorough degranulation and root planing.

The area is rinsed with sterile saline. Examination of the defect and adjacent root surfaces should be performed to detect pathological conditions such as root fracture, severe root irregularities, cemental pearls or cervical enamel projections not easily removed by odontoplasty, root caries or subgingival and/or open restoration margins at the CEJ. These abnormalities must be successfully treated prior to proceeding or the subject will be excluded from the study.

Direct measurements of the intra-bony defect will be performed, as soon as the defect is thoroughly debrided, using a calibrated probe scoring the following dimensions:

- vBD (must be 4 mm or greater);
- W, the width of the defect from the root surface to the farthest bone wall; and
- The predominant number of bone walls present (i.e. 1-3)

At this point, final eligibility of the target tooth will be confirmed on the basis of the acceptable depth of the defect and the number of bone walls.

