If the target tooth does not meet the inclusion criteria, the tooth will not receive the study treatment and standard care will be provided. If additional target teeth were identified during the screening process, the previous steps (up to determination of the final eligibility) will be performed on the next target tooth in order of ranking until a target tooth is deemed eligible or all have failed to meet the eligibility criteria. If all target teeth fail to meet the eligibility criteria, complete the Screening Failure Log and provide standard care.

If the target tooth meets the eligibility criteria, the steps below will be followed. Note that only one tooth per subject may receive treatment with the investigational product.

Decorticate cleaned defect with small round bar, and add neutral EDTA to condition the roots. The EDTA should be carefully applied to the tooth root surface with a small brush or other instrument avoiding excessive running of the paste onto the bone surfaces. After two minutes, the EDTA is removed using irrigation and suction.

Randomization

The subject is randomly assigned to a treatment group and the specified investigational device kit identified by the sequential product numbers on the label of the box is retrieved.

Implantation:

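### The ordinal baseline comparison in section 12.1.6 is planned on a variable that equals one for every subject, so it can never show an imbalance (minor)

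*Protocol*

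**What the plan says.** Section 12.1.6 sorts baseline characteristics into three types, each with its own test across the four arms. Continuous ones: "continuous baseline characteristics (i.e. age, percent bone required to be regenerated) will be analyzed using ANOVA". Categorical ones (gender, race and smoking history are named) go to a generalized Fisher exact test. For ordinal ones it says: "Differences between ordinal outcomes (i.e. number of teeth to be implanted) will be analyzed using a singly ordered exact Kruskal-Wallis test". Any baseline covariate found imbalanced at the 0.05 level is then added to sensitivity models, logistic for binary endpoints and ANCOVA for continuous ones. Sections 12.1.8 and 12.1.9 repeat that rule.

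The number of teeth treated is fixed elsewhere. Section 8.1: "one eligible tooth will be selected to receive the study treatment". Section 8.3.4: "Note that only one tooth per subject may receive treatment with the investigational product". Section 8.3.1 carries the same limit, and sections 8.3.5 and 8.3.6 rule out any further implantation during follow-up.

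The defect is measured during surgery, and section 8.3.4 lists among the measurements "The predominant number of bone walls present (i.e. 1-3". Entry requires a "4 mm or greater intrabony defect with at least 1 bony wall" (section 6.1). Section 5.2.1 gives the timing: "The randomization will be performed intraoperatively after surgeons confirm if the probing bone depth and the number of bony wall of defect".

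**The concern.** A baseline comparison is useful only if the variable can differ between subjects. The one ordinal variable named in section 12.1.6 cannot, because the design sets it to one. The planned test is therefore carried out and reported but carries no information.

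The trial does record an ordinal feature of the defect before randomization, the number of bone walls, and section 12.1.6 does not mention it. The protocol treats defect form as relevant: walls are an entry criterion, and section 8.3.3 ranks candidate teeth by defect depth and angle. Randomization is stratified by smoking and balanced within site, not by defect features, and the primary logistic model adjusts only for age and smoking.

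The same section also names "percent bone required to be regenerated" as a continuous characteristic, but no formula or measurement for it appears anywhere in the protocol.

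What is at stake is how well the baseline comparison describes the defects, and which covariates reach the sensitivity models.

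**Working it through.** The plan gives no figure on this point to reproduce. The check has four steps.

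**1. The value of the variable.** Sections 8.1, 8.3.1 and 8.3.4 allow one treated tooth per subject. Section 12.1.3 defines the ITT population as randomized patients who receive the study therapy. Every subject in that population therefore has the value 1.

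**2. The test on a constant.** Take N = 94 randomized (section 5.1), split 24/24/23/23 for illustration.
- With all values tied, every rank is (N + 1)/2 = 95/2 = 47.5, so every arm's mean rank is 47.5.
- The Kruskal-Wallis numerator is 12/[N(N + 1)] × Σ nᵢ(mean rankᵢ − 47.5)² = 0.
- The tie correction is 1 − (N³ − N)/(N³ − N) = 0, so the large-sample statistic is 0/0 and undefined.
- The protocol specifies the exact test. Every reallocation of subjects to arms gives the same value as the one observed, so the share of reallocations at least as extreme is 1, and p = 1.
- Since p = 1 always exceeds 0.05, the chance of a flag is 0%, whatever the split.

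**3. The same test on number of bone walls.** This variable can take the values 1, 2 or 3. The protocol gives no distribution of walls, so the shares below are assumptions. The simulations use the large-sample version of the test, 20 per arm, 4,000 repeats each.

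| Assumed shares of 1/2/3 walls | Flagged at 0.05 |
|---|---|
| 20/40/40% in all arms | 4.8% |
| 33/34/33% in all arms | 4.6% |
| 10/30/60% in all arms | 4.4% |
| 50/30/20% in one arm, 20/40/40% in the other three | about 52% |

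On walls the test behaves as a test should. Even so, it misses the large imbalance in the last row in about 48% of trials (100 − 52).

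**4. Percent bone.** Section 8.1.3.3 records three baseline radiographic lengths: A0 (root length), B0 (CEJ to base of defect) and C0 (CEJ to crest). A baseline percentage that varies between subjects can be formed from them, for example (B0 − C0)/A0. That ratio is only an illustration; the protocol does not say which ratio is meant.

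**The case against.** Four things can be said against making more of this.

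**Walls are unnamed, not barred.** A reader might infer that wall number goes unchecked, or that a difference in defect form could never bring in a sensitivity model. The text does not support that. The rule in section 12.1.6 refers to any baseline covariates, and sections 12.1.8 and 12.1.9 to any additional ones found imbalanced. The protocol also uses 'i.e.' loosely to introduce examples (sections 8.1.2 and 8.1.3.3), so the lists in parentheses need not be closed. A full list of baseline variables is often left to the SAP, which is not shown. This objection stands.

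**Percent bone is undefined, not useless.** A reader might equate it with the percent bone fill of section 8.1.3.3 and conclude that it is 100% for everyone at baseline. That formula is a follow-up outcome, and other denominators are on record. This also stands; a definition is all that is needed.

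**The test does return a result.** One might say that it yields no p-value. That is true of the large-sample version, not of the exact test the protocol names, which yields 1.

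**Swapping the variable gains little on its own.** With 23 per arm and an assumed 15 to 30% share of 1-wall defects, chance alone makes some dose differ from control by 20 points or more in that share in about 15 to 33% of trials. Kruskal-Wallis on walls flags only about 13 to 16% of those trials. This stands too, and it is the reason to put walls in a sensitivity model without waiting for a significant balance test.

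None of this removes the contradiction. A longer list in an SAP would leave section 12.1.6 planning a test on a constant.

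**Conclusion.** The point holds as a minor error of wording with a certain consequence: the ordinal comparison named in section 12.1.6 has p = 1 in every possible outcome of the trial. This follows from the protocol alone and needs no assumption.

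Its reach is limited. It affects the baseline comparison and, through it, the choice of covariates for sensitivity models. The primary model (section 12.1.8) has fixed covariates, the dose-selection contrasts (section 12.1.10) do not use the balance tests, and the sample size (section 12.1.2) rests on bone-growth means and SDs and on dropout. The secondary ANCOVA models already adjust for the endpoint's own baseline value. Section 12.1.1 adds that this is a feasibility study without formal tests for approval or labeling.

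A reader might wish to put a size on the bias in the success difference from an imbalance in walls. The documents give neither the distribution of walls nor their effect on success, so no such figure is supported. The flag rates shown for walls depend on assumed shares and serve only to show that the test becomes informative.

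**What to change.** In section 12.1.6:
- Replace the number of teeth implanted with number of bone walls (1, 2, 3) as the ordinal baseline variable. If the number of target teeth identified before surgery was meant, which can vary between subjects (sections 8.3.1 and 8.3.3), say that instead.
- State that number of bone walls enters a sensitivity model alongside age and smoking, logistic for the composite endpoints and ANCOVA for the continuous ones, whatever the p-value of the balance test.
- Define the percent-bone variable by a formula in A0, B0 and C0.

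The cost is a few sentences. Wall number and the three radiographic lengths are already planned measurements, and walls are assessed before randomization, so no visit, form or subject is added. The primary analysis stays as it is.

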12.1.7 Missing Data Strategies

Given the nature of the study, very few dropouts (<5%) are expected. This is a consequence of the close bond that develop between study Investigator teams and their patients, which will be observed and reinforced through the Study Monitors assigned to respective sites. In the event that there are any missing data, the percents with missing data will be compared using a two-sided Fisher Exact test; the reason for withdrawal will be presented to see if any treatment group or site pattern exists. While the primary analysis will be based on all available data with no imputation performed, sensitivity analyses will be performed to assess the potential impact of missing data.

This will include an analysis where missing data is treated as a success, an analysis where missing data is treated as a failure, and finally an analysis where missing data in the control group is treated as a success and missing data in the GFeBGS group is treated as a failure.

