6.4 Criteria of Failures (Discontinuation or Withdrawal of a Subject)

The primary reason for discontinuation or withdrawal of the subject from the study should be recorded on the Subject Discontinuation/Withdrawal form (CRF 10) using the following categories:

1. Pre-treatment event or adverse event (AE). The subject has experienced a pre-treatment event or AE that requires early termination because continued participation imposes an unacceptable risk to the subject's health or the subject is unwilling to continue because of the pre-treatment event or AE.
2. Major protocol deviation. The discovery post-randomization that the subject failed to meet protocol entry criteria or did not adhere to protocol requirements, and that continued participation would pose an unacceptable risk to the subject's health.
3. Lost to follow-up. The subject did not return to the clinic and attempts to contact the subject were unsuccessful. Attempts to contact the subject must be documented.
4. Voluntary withdrawal. The subject (or subject's legally acceptable representative) wishes to withdraw from the study. The reason for withdrawal, if provided, should be recorded in the CRF.

Note: All attempts should be made to determine the underlying reason for the withdrawal and, where possible, the primary underlying reason should be recorded (i.e. withdrawal due to an AE should not be recorded in the “voluntary withdrawal” category).

5. Study termination. The Sponsor, IRB or regulatory agency terminates the study.
6. Subject does not meet eligibility requirements at Visit 5 and has not signed the informed consent for enrollment in the study.
7. Unexpected surgery is required including rescue treatment of the target tooth.
8. Excluded medication is required including rescue treatment of the target tooth.
9. Unexpected amount of loss of the device from the target tooth.
10. Unacceptable safety risk develops.
11. Other. Note: The specific reasons should be recorded in the “specify” field of the CRF.

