8.3.6 Visits 8 and 9: Subsequent Follow-up or Early Termination Evaluations

Subsequent follow-up visits occur at 3 and 6 months (final evaluation) post-surgery (\pm one week). During these visits, photographs are taken and the endpoint measurements of clinical attachment level (CAL), probing pocket depth (PD) and gingival recession (GR) will be assessed in the surgery site. Subjects with an increase of specific antibody production against rh-bFGF at Visit 7 will have blood serum collected until their results return to baseline values. Deep scaling of the target tooth should not be performed for the duration of the study and no additional implantation of the investigational product is allowed. Note that this visit is also conducted for early termination. Note that if a subject is diagnosed with a precancerous lesion such as leukoplakia after the study starts, it will be biopsied as appropriate for further analyses. A summary of all procedures to be performed is listed below:

Summary of Procedures/Measurements:

- Detailed probing measurements of the target tooth including:
 - CAL (calculation)
 - PD
 - GR
 - BOP
- Photographs of surgical site
- Routine supragingival prophylaxis
- Standardized PA radiograph of surgical site (see Section 8.1.3)
- Only at 3 months post-implantation: Oral hygiene instruction and full-mouth prophylaxis for staining due to CHX rinse or swab
- Record tobacco use on the Subsequent Follow-up Evaluation form (CRF 6)
- Concomitant medication review, especially number and type of analgesics since the last visit
- Complete the Subsequent Follow-up Evaluation form (CRF 6)
- Adverse Events review. Complete the Adverse Events form (CRF 8) if necessary
- If necessary, collect blood serum sample for rh-bFGF antibody

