10.2 Visit Boundaries and Missed Visits

Figure 5 defines the tolerance range for each follow-up visit. A visit that occurs outside of the specified range will be coded using the closest follow-up window and identified as a protocol deviation on the Protocol Deviation form (CRF 9).

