12.1.5 Patient and Visit Deviations

Patients will be evaluated to assess eligibility, treatment compliance, visit compliance, and other protocol deviations such as excessive smoking, poor dental care, concurrent medical conditions impacting effectiveness or safety evaluations, and missed visits. Any post-baseline visits occurring more than two weeks outside of study visit windows will be reported. Withdrawals due to lack of effectiveness or adverse events will also be reported as well as the timing of such events. Dropouts will also be reported as well as the nature and timing of such dropouts for any reason. A 15% allowance has been made for dropouts; treatment assignments for dropouts will not be recycled. All patients will be included in all analyses to the fullest extent possible; no data will be carried forward.

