12.1.9 Secondary Effectiveness Analysis

Superiority will be tested for the continuous effectiveness endpoints (e.g. Δ CAL, LBG, %BF, PD) using an ANCOVA model with the same baseline covariates as specified above and in addition, the corresponding baseline value for each endpoint. The ANCOVA model will include the same covariates as for the primary effectiveness endpoint. The two-sided 95% lower bound for the LSMEAN difference between each of the three GFeBGS treatment groups minus Active control will need to exceed 0 to achieve superiority.

Additional ANCOVA models will also evaluate any additional covariates found to be imbalanced ($p \leq 0.05$) at baseline.

Effectiveness outcomes will be displayed at every visit in order to characterize the time of onset and duration of effectiveness throughout the study. Results will be displayed for subjects who complete the study as planned as well as for those withdrawn early; the patterns of withdrawal will be displayed for each study treatment group to assess if reasons withdrawn were different in any respect.

Analyses will also be conducted for the other effectiveness endpoints inclusive of PDR, GR, WH, and BOP; the second composite endpoint (Δ CAL, %BF) will be analyzed in the same manner as for the first composite endpoint. In general, for continuous variables, the mean, median, standard deviation, minimum and maximum values will be displayed; for ordinal and categorical variables,

CONFIDENTIAL

frequencies and percentages will be displayed. When relevant, the mean changes from pre-operative baseline will be computed for all treatment groups at each visit through study exit; an unpaired t-test will be used to test for improvement between the treatment groups while a paired t-test will be used to test for improvement within the treatment groups. Superiority will be tested for continuous outcomes using an unpaired t-test by examining the two-sided 95% lower bound for the difference between GFeBGS minus Active control to test if the lower bound exceeds 0. The percents achieving predefined effectiveness milestones will be displayed at each post-baseline time through each stage; a two-sided Fisher Exact test will be used to test for superiority.

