12.1.10 Dose Selection

Dose selection for future study will be based on an analysis of the primary composite endpoint. Five different dose response patterns will be examined and modeled statistically, with the dose selected based on the best model fit. Specifically, we will perform a logistic regression of the primary composite endpoint and apply linear contrasts to the model according to the following five dose response patterns for success:

1. An increase in a linear manner from the Treatment I to Treatment IV groups
2. A plateau in the Treatment II group, with similar performance in groups II through IV
3. A plateau in the Treatment III group, with similar performance in group IV
4. An apex in the Treatment III group; best performance in group III, lower performance in the other groups
5. An apex in the Treatment IV group; best performance in group IV, lower performance in the other groups

For each contrast, the Wald test statistic will be computed and the pattern that corresponds to the largest value of the Wald statistic will be considered the best fit and guide the selection of the optimal dose.

For patterns where there is insufficient data to distinguish between effective doses, patterns 2 and 3 for example, the 0.3% rh-bFGF dose may be selected based on prior data and pre-clinical testing.

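### No rule counts a rescued target tooth as non-success: without a six-month value it leaves the denominator of the primary and dose-selection analyses, and a post-rescue value may count as measured

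*Protocol*

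**What the plan says.** **Missing data.** Section 12.1.7 sets the primary rule: "While the primary analysis will be based on all available data with no imputation performed, sensitivity analyses will be performed". Section 12.1.5 adds: "All patients will be included in all analyses to the fullest extent possible; no data will be carried forward". Three sensitivity analyses follow in 12.1.7: missing as success, missing as failure, and missing as success in control but as failure under GFeBGS. That section also plans a Fisher test of missingness and a listing of reasons for withdrawal.

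**Rescue.** Two of the withdrawal reasons in 6.4 are "Unexpected surgery is required including rescue treatment of the target tooth" (item 7) and "Excluded medication is required including rescue treatment of the target tooth" (item 8). The section title speaks of criteria of failures, but no analysis section uses that term.

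**Endpoint and population.** Success needs ΔCAL of at least 1.5 mm and LBG of at least 1 mm at six months (5.2.2, 12.1). Rescue is not part of the definition. The ITT population for the primary analysis (12.1.3) is everyone randomized and treated, so it includes rescued subjects.

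**Termination visits.** Section 8.3.6 says of Visits 8 and 9: "Note that this visit is also conducted for early termination". Under 10.2, a visit outside its range "will be coded using the closest follow-up window and identified as a protocol deviation".

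**Dose selection.** Section 12.1.10 says: "Dose selection for future study will be based on an analysis of the primary composite endpoint". It gives no missing-data rule of its own.

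**Display.** Section 12.1.9 adds: "Results will be displayed for subjects who complete the study as planned as well as for those withdrawn early", with patterns of withdrawal by arm.

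**The concern.** A missed visit may have nothing to do with how the tooth is doing. Rescue of the target tooth usually does: it suggests that the study treatment was not enough. An available-case rule treats the two alike. A rescued tooth without a six-month value is removed, and the success rate among the teeth that remain goes up. If rescue is more common in one arm, that arm looks better than it is, both against control and in the five contrasts used to choose a dose.

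The termination visit opens a second, narrower route. If a measurement made after rescue is coded to month 6, nothing stops it from entering the composite as if it reflected the study treatment alone. None of the planned missing-data analyses would touch it, because it is not missing.

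What is at stake is the reading of the dose-response pattern from about 23 subjects per arm. No labeling claim depends on it.

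**Working it through.** **Inputs from the protocol.** There are 94 subjects in four equal arms, so 94/4 = 23.5, taken as 23 per arm. Expected dropout is under 5% in 12.1.7 (94 × 0.05 = 4.7 subjects, all reasons), while 5.1, 12.1.2 and 12.1.5 allow 15% (94 × 0.15 = 14.1). The plan's own sample-size figure concerns LBG. It reproduces (80.8% power at 20 per arm, SDs 1.20 and 2.30 mm, difference 1.70 mm) but says nothing about the composite.

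**Inputs assumed.** The protocol gives no rescue rate and no composite success rate. All counts below are illustrations.

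**1. Rate within an arm.** If s is the success rate with rescued teeth counted as non-success and r is the fraction removed, the available-case rate is s/(1 − r). With 12 successes of 23:

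| Rescued teeth dropped | Reported rate | Shift in points |
|---|---|---|
| 0 | 12/23 = 52.2% | 0 |
| 1 | 12/22 = 54.5% | +2.4 |
| 2 | 12/21 = 57.1% | +5.0 |
| 3 | 12/20 = 60.0% | +7.8 |

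**2. Difference from control.** Take 12/23 active and 9/23 control. Counting rescue as non-success gives 52.2 − 39.1 = 13.0 points.
- Three rescues, all active, dropped: 60.0 − 39.1 = 20.9.
- Three rescues, all control, dropped: 52.2 − 45.0 = 7.2.
- Three rescues in each arm, dropped: 60.0 − 45.0 = 15.0.

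Uneven rescue moves the difference far more than even rescue does.

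**3. Dose-response contrasts.** For each arm, logit = ln(s/(n − s)) and variance = 1/s + 1/(n − s), with s here the number of successes. Wald chi-square = (Σc·logit)² / Σc²·variance. The contrasts are assumed: pattern 1 (−3, −1, 1, 3) and pattern 2 (−3, 1, 1, 1). Assumed successes are 8, 12, 15, 15 of 23 in Treatments I to IV.
- Rescue counted as non-success: the logits are −0.629, 0.087, 0.629, 0.629, and the variances are 0.1917, 0.1742, 0.1917, 0.1917. Pattern 1: 4.313²/3.816 = 4.88. Pattern 2: 3.230²/2.283 = 4.57. Pattern 1 leads.
- Two rescued subjects dropped from Treatment II (n = 21): its logit becomes 0.288 and its variance 0.1944. Pattern 1: 4.113²/3.836 = 4.41. Pattern 2: 3.431²/2.303 = 5.11. Pattern 2 leads.

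Scoring pattern 1 by actual dose (−2, −1, 1, 2) gives the same switch: 4.92 against 4.57, then 4.25 against 5.11. Pattern 3 does not lead in either case (4.32, then 3.32), and patterns 4 and 5 stay at or below 1.42.

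This example is a near-tie. Changing one success in one arm gives eight neighbouring cases. The switch holds in five; in two, pattern 2 already leads; in one, pattern 1 stays ahead.

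**4. How often.** Trials were simulated with 23 per arm and true success of 8/12/15/15 or 6/8/12/12 of 23, dropping non-successes from one arm at a time.
- One dropped: the leading pattern changes in about 5% to 11% of trials.
- Two dropped: about 10% to 22%.
- Indicated dose, taking patterns 1 and 5 as Treatment IV and patterns 2, 3 and 4 as Treatment III (12.1.10 allows 0.3% for patterns 2 and 3): about 3% to 9% with one dropped, 5% to 17% with two.

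**5. How likely are two rescues in one arm?** The binomial P(at least 2 of 23) is 7.7% at an assumed 2% rescue rate and 32.1% at 5%. The second figure puts rescue alone at the ceiling that 12.1.7 expects for dropouts of every kind.

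**The case against.** **The protocol does not say that rescued teeth are removed.** A reader might infer that every rescued tooth leaves the analysis. The documents do not support that. Under 6.5 termination is something the investigator may do, the Early Termination procedures are to be attempted, and Visit 9 includes probing and a standardized radiograph. A rescued tooth can stay in at its measured value. Nor is there a fixed cut-off: week 18, midway between weeks 12 and 24, is only an inference from 10.2, which does not mention early termination. This objection stands, and it limits the denominator point to subjects with no value coded to six months.

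**The SAP could settle it.** The SAP was not available for this review, and it could define rescue as non-success without calling that imputation. That is fair. But the protocol already fixes available-case handling for the primary analysis and reads dose selection from the same composite, so the point addresses a stated rule rather than a missing detail.

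**Missing-as-failure is already planned.** For subjects with no six-month value it gives the proposed result in the primary comparison, and the reports of withdrawals by arm would help expose a pattern. This largely stands. However, that analysis also fails ordinary losses, cannot correct an observed post-rescue value, and is not tied to 12.1.10.

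**Items 7 and 8 are broad.** Item 8 could catch an excluded drug taken for another purpose, such as an NSAID for post-surgical pain (6.3.1). Scoring all such subjects as non-success would discard valid six-month outcomes. This stands, and the fix is restricted accordingly.

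**The trial is exploratory.** There is no labeling use, the leading pattern only guides the choice, and the Sponsor may take any active dose forward. This stands and lowers the priority.

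**Conclusion.** The point holds in limited form. A subject withdrawn for rescue of the target tooth and lacking a six-month value drops out of the primary composite in 12.1.8 and 12.1.10. A post-rescue termination measurement coded to month 6 may count as measured. In neither case does a rule score the tooth as non-success.

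The size cannot be derived from the protocol. The figures above rest on assumed success counts, assumed rescue counts, 23 per arm and assumed contrast scores. In those scenarios one or two exclusions from a single arm leave the leading pattern unchanged in most trials, and the indicated dose changes less often still. A reader might infer from the worked example that dose selection is likely to go wrong. It does not show that: it was a near-tie and fails to switch in three of eight neighbouring cases.

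This is a low-priority but cheap improvement to the analysis rules.

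**What to change.** Change analysis wording only; withdrawal criteria and clinical rules stay as they are. In 12.1.7, 12.1.8 and 12.1.10:

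- Count a subject as non-success on the primary composite when surgery or medication was given as rescue treatment of the target tooth before the six-month assessment.
- Do not use measurements taken after such rescue as six-month values.
- Do not apply this to other surgery, or to excluded medication taken for other reasons such as post-surgical analgesia. Keep those subjects at their observed six-month values.
- Keep available-case handling, with the planned sensitivity analyses, for all other losses.

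The cost is a few sentences and one check of the form: CRF 10 records the reason for withdrawal, but must show whether an item 7 or 8 event was rescue of the target tooth. Reported success rates will be slightly lower. The planned sample size does not change.
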